11.0 DATA REPORTING / REGULATORY REQUIREMENTS

11.1 Ethical and Regulatory Considerations

This trial will be conducted in compliance with the protocol, Good Clinical Practice guidelines, and all applicable regulatory requirements.

11.2 Institutional Review Board

The Principal Investigator will have obtained written approval to conduct the study from The Ohio State University IRB and the Clinical Scientific Review Committee of the James Cancer Hospital and Solove Research Institute. All amendments must be approved by the Institutional Review Board of The Ohio State University prior to implementation.

11.3 Informed Consent

All potential candidates for the study will be given a copy to read of the consent form for the study. The Principal Investigator and/or designee will explain all aspects of the study in lay language and answer all the candidate's questions regarding the study. If the candidate desires to participate in the study, he or she will be asked to sign the Informed Consent. The study agent will not be released to a subject without a signed Informed Consent. Elements of informed consent include explanations of 1) the purpose of the trial, 2) what the study entails, 3) alternate treatments, 4) expenses and inconveniences to be incurred, 5) discomfort and risks to the subject, 6) whether she will receive payment for participation in the study, 7) contact person to call in the event of an emergency, 8) subject rights as a result of illness or injury from trial

[Type here]

participation, 9) subjects right to withdraw from the trial at any time without prejudice, 10) confidentiality of trial participation.

11.4 Patient Confidentiality

The information obtained during the conduct of this study is considered confidential and will not be released without the written permission of the subject, except as necessary for regulatory agencies. Signed consent forms, data sheets, and laboratory notebooks will be kept in locked cabinets in Clinical Trials Office at Stefanie Spielman Breast Center.

11.5 Publication and Research Findings

Publications of the research findings will present data in a format that will not reveal the identity of the participants.

11.6 Compliance Monitoring

In accordance with IRB guidelines, the study program will be reviewed by the IRB every 12 months or less. Deviations from the protocol must be documented in the medical record and reported immediately to the PI. Deviations that meet the criteria for Immediate Event Reporting (<http://orrrp.osu.edu/irb/event/index.cfm>) such as those that increase risks to subjects and/or compromise scientific integrity will be reported immediately to the IRB.

11.7 Data Safety Monitoring

The data and safety monitoring plan will involve the continuous evaluation of safety, data quality and data timeliness. Investigators will conduct continuous review of data and patient safety at their regular Disease Group meetings (at least monthly) and the discussion will be documented in the minutes. The PI of the trial will review toxicities and responses of the trial where applicable at these disease center meetings and determine if the risk/benefit ratio of the trial changes. Frequency and severity of adverse events will be reviewed by the PI and compared to what is known about the agent/device from other sources; including published literature, scientific meetings and discussions with the sponsors, to determine if the trial should be terminated before completion. Serious adverse events and responses will also be reviewed by the OSUCCC Data and Safety Monitoring Committee (DSMC). The PI will also submit a progress report biannually that will be reviewed by the committee per the DSMC plan. All reportable Serious Adverse Events (SAE) will also be reported to the IRB of record as per the policies of the IRB.

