1.1 Trial Design

This study is a randomized, crossover, non-placebo controlled trial of 50 patients with history of breast cancer and bothersome hot flashes. We propose to have 25 patients per arm in a two-arm study randomized to Embr Wave device vs no device or other treatment for bothersome hot flashes with a 1-month crossover. *The study has enrolled 23 participants with no active subjects in follow up as of 01/05/2022. The current amendment version dated 1/5/2022 includes the following changes a) update the study intervention to recently launched Embr Wave Generation 2 device and b) enroll an additional 10 participants so that approximately 50% of the study population will use the Generation 2 device. This increases initial planned sample size of n=40 by an additional 10 subjects to n=50. Study design shown below in Figure 1.*

[Type here]

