2.0 TRIAL OBJECTIVES

This study will evaluate the preliminary efficacy of the EMBr Wave wrist device in managing the symptoms of hot flashes in patients with a history of breast cancer who have been experiencing hot flashes for at least 30 days prior to study entry. This study is based on published data that this device can improve thermal comfort by producing varying temperature pulses to counter uncomfortable sensations of heat or coolness.

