3.2 EMBr Wave Device

While there are non-hormonal medical options to treat hot flash for breast cancer survivors, this study is investigating the use of a personalized cooling mechanism for hot flash relief. The EMBr Wave device has not previously been tested in clinical studies in breast cancer, but shows novel and promising hot flash relief for this unique population, possibly allowing for hot flash reduction without the use of an oral medication. The EMBr Wave device (both Generation 1 and 2) works by delivering heating or cooling pulses through the wrist bracelet. Because of the wrist's sensitivity to temperature, these pulses can be used to promote overall comfort despite other uncomfortable temperature sensations affecting the entire body. Users simply press either the cooling or heating button depending on which sensation they desire. The Generation 2 Embr Wave device has the same functionality as the Generation 1 device, but with an improved smaller design. A graphical design of the devices is shown in Figure 2.

[Type here]

Figure 2: EMBR Wave Generation 1 Device (top) and Embr Wave Generation 2 Device (bottom)

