4.5 Study Intervention

EMBr Wave devices will be worn by study participants during the daytime and nighttime during the treatment periods of the trial. Participants will be asked to use the device as needed during the daytime and nighttime for management of hot flashes and night sweats. Participants will be asked to complete the hot flash assessments described above. Because hot flashes are transient and the EMBr Wave device is not expected to modify the underlying condition, a carry-over effect is unlikely in the crossover design. Due to the unlikelihood of carry-over and to avoid unnecessarily increasing patient burden, we will not use a wash-out period.

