5.0 POTENTIAL TOXICITY, DOSE MODIFICATIONS, AND MANAGEMENT

Because EMBr Wave is a superficial, non-invasive device, we expect to see very little or no toxicities at all that are seen in its chronic use. Regardless, we will monitor for them. The severity of adverse reactions is categorized from grade 1 to grade 5 in increasing severity.

Table 4. General descriptors for the toxicity grades, ranged from mild to fatal.

Grade 1	Mild – the adverse reaction does not interfere in a significant manner with the subject’s normal functioning level. It may be an annoyance.
Grade 2	Moderate – the adverse reaction produces some impairment of functioning but is not hazardous to health. It is uncomfortable and/or an embarrassment
Grade 3	Severe – the adverse reaction produces significant impairment of functioning or incapacitation and is a definite hazard to the subject’s health
Grade 4	Severe – adverse reactions that include or lead to either a) a life-threatening event, though acute and without permanent effect, b) prolonged inability to resume usual life pattern, or c) impairment of ability to adequately deal with future medical problems
Grade 5	Death related to AE

Toxicity will be monitored during study visits and telephone calls using the National Cancer Institute Common Terminology Criteria for Adverse Events version 5.0 (CTCAE) of the National Cancer Institute will be used:

[Type here]

(https://ctep.cancer.gov/protocoldevelopment/electronic_applications/docs/CTCAE_v5_Quick_Reference_5x7.pdf). Grade 3, 4 and 5 toxicities that are related to the study will be reported as adverse events.

Patients with Grade 3-4 adverse reactions that are related to the study will be removed from the study.

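### Adverse events are compared only with outside knowledge of the device; the randomised no-device month goes unused as a concurrent control for general symptoms

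*Combined protocol and SAP*

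**What the plan says.** Section 11.7 has the principal investigator review the frequency and severity of adverse events, "compared to what is known about the agent/device from other sources", with the sources and purpose given as "including published literature, scientific meetings and discussions with the sponsors, to determine if the trial should be terminated before completion". It gives no outside rate and no threshold. The same section provides for review at disease group meetings at least monthly, a judgement on whether risk and benefit have changed, DSMC review of serious events, and a progress report to the DSMC twice a year.

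On outside evidence, Section 3.2 states: "The EMBr Wave device has not previously been tested in clinical studies in breast cancer". Section 2.0 does cite outside work, "This study is based on published data that this device can improve thermal comfort", but that concerns comfort and gives no adverse event rate. Section 5.0 says "we expect to see very little or no toxicities at all that are seen in its chronic use", again without a figure.

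On design, Section 1.1 describes women "randomized to Embr Wave device vs no device or other treatment for bothersome hot flashes with a 1-month crossover", and the calendar in Section 7.2 gives each sequence 28 days with the device and 28 without. The sample size is 50: "This increases initial planned sample size of n=40 by an additional 10 subjects to n=50". Section 4.5 adds "we will not use a wash-out period".

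Section 12.1 fits its treatment and period model to the HFRDIS and the daily hot flash score. It contains no analysis or summary of adverse events, and no other section compares events between the two periods.

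**The concern.** Women in this trial may be taking tamoxifen, an aromatase inhibitor, anti-HER2 therapy, an SSRI or SNRI, or gabapentin or pregabalin (Section 4.1.2). These can bring symptoms of their own. A count of general symptoms during the device month therefore mixes any device effect with a background that may differ from that of the people behind the outside sources. If the background here is higher, a harmless device can look worse than expected. If it is lower, a real excess can look normal. Attribution by the investigator helps, but the trial is unblinded and attribution is a judgement on single events, not an estimate of the background.

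The no-device month estimates that background in the same women, under randomised order. At stake is the tolerability information carried forward. The secondary objectives and the close of Section 12.1 both say that the data will inform larger trials.

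**Working it through.** The documents give no adverse event rate, stopping threshold or safety power, so there is no stated figure to reproduce. The check has a textual part and an illustration under assumed rates.

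**Text set side by side**

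- *Comparator.* Section 11.7 names outside sources only. Section 12.1 names none, because it plans no adverse event summary.
- *Concurrent control.* Sections 1.1 and 7.2 provide 28 no-device days per woman, or 50 × 28 = 1,400 woman-days if all complete.
- *Is capture equal in both months?* This is not assured. Section 5.0 reports as adverse events only related toxicities of grade 3 to 5. Section 9.0 defines an event by its timing relative to use of a treatment or procedure. Section 9.3 collects all events, in text about gait and neuropathy. Section 7.1 provides for calls that may ask about problems with the watch, which points towards device months. Section 11.10 relies on self-report and names no period.
- *Can events be assigned to a month?* Sections 9.2 and 11.12 list type, duration, grade, suspected cause and response (11.12 adds actions taken). Onset date is in neither list.

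**Why the comparator matters (assumed rates)**

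Suppose the outside benchmark is that a proportion b of women have an event in a month, and a count is called high at the smallest k with P(X ≥ k) ≤ 0.05 for X ~ Binomial(50, b). The table gives the chance that a harmless device reaches k when the women's own monthly background is p.

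| Benchmark b | k of 50 | p = 5% | p = 10% | p = 20% | p = 30% |
|---|---|---|---|---|---|
| 2% | 4 | 24% | 75% | 99% | >99% |
| 5% | 6 | 4% | 38% | 95% | >99% |
| 10% | 10 | <1% | 2% | 56% | 96% |

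The error can also run the other way. A device that doubled a true background of 5% to 10% would be flagged against a 10% benchmark only 2% of the time (last row, p = 10%). Section 11.7 prescribes no such limit; the table only shows how far the reading depends on the match between benchmark and background.

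**What the no-device month could add (assumed rates)**

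With n complete pairs, equal event proportions p in both months and independence between months, the 95% half-width for the within-woman difference is 1.96 × √(2p(1 − p)/n).

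- n = 50, p = 10%: 1.96 × √(0.18/50) = 0.118
- n = 50, p = 20%: 1.96 × √(0.32/50) = 0.157
- n = 27, p = 10%: 1.96 × √(0.18/27) = 0.160
- n = 27, p = 20%: 1.96 × √(0.32/27) = 0.213

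The case n = 27 is 50 − 23, because Section 1.1 says that 23 women had been enrolled, with none active, at the amendment. It applies if equal capture can be assured only from now on. Women who tend to report in both months would make the intervals narrower; drop-out would make them wider.

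Exact two-sided McNemar power with 50 independent pairs:

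| Background | 10-point excess | 20-point excess | 30-point excess |
|---|---|---|---|
| 10% | 20% | 63% | 92% |
| 20% | 15% | 50% | 84% |

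**The case against.** The strongest reply is that Section 11.7 describes normal practice. Comparing a device's events with what is known about that device is what monitors do, and being untested in breast cancer does not mean that no outside data exist. A reader might infer from Section 3.2 that no outside source is relevant, so that the comparison is invalid. The documents do not support that: Section 2.0 cites published work on the device, and knowledge of local effects can carry over from other users.

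A reader might also infer that early termination turns on a raw device-month count set against the literature. The text does not say so. Section 11.7 also has risk and benefit review and DSMC oversight, Section 9.1 sets five levels of attribution, and Sections 9.2 and 11.12 ask for suspected cause, naming concurrent medication and illness. Nor does the plan rule out an internal comparison; it is silent.

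Two further points stand. For a wrist device, local skin reactions are an obvious concern. Their no-device rate is near zero by construction, so the control month adds little there, and serious events will be too few to compare. And the paired table cannot simply be drawn from the data as planned, because onset date is not a listed field and equal capture is not settled. A within-woman difference computed without those repairs could be biased while looking rigorous.

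What remains is narrower. For general symptoms, a randomised concurrent control exists, and no section uses it.

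**Conclusion.** The point holds as a low-cost improvement. Section 11.7 looks only outward for its comparator, Section 12.1 has no adverse event summary, and the no-device month could supply a better reference for general symptoms in a population in which the protocol says the device is untested. It is not an error in the monitoring plan, and nothing here shows that the plan would miss harm or stop wrongly.

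The benefit is limited. Under assumed backgrounds of 10% to 20%, the interval is about ±12 to ±16 points with 50 complete pairs, or about ±16 to ±21 with the 27 women not yet enrolled at the amendment. Only large differences would show, so it would be wrong to infer that the table could serve as a safety test. These figures rest on assumed event proportions and independence between months; no rate comes from the documents. Unblinded self-report could inflate device-month events, and with no wash-out a late device reaction in Group A could fall in the no-device month.

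**What to change.** 1. Reconcile Sections 5.0, 9.0 and 9.3, and state that adverse events are collected in the same way, with the same prompts, in both 28-day periods.
2. Add onset date to the fields listed in Sections 9.2 and 11.12. For the 23 women already enrolled, say whether onset can be recovered from the medical record, and mark their data if it cannot.
3. In the DSMC progress report and in Section 12.1, tabulate the number and proportion of women with an event by device and no-device period, and by sequence, grade and attribution.
4. Show local wrist and skin events separately. Show Group A events that start after device return separately, with the time window fixed in advance, so that late device reactions are not counted as background.
5. In Section 12.1, give the within-woman difference with a 95% interval, labelled descriptive, with the number of complete pairs. State that it sets no stopping rule.
6. Keep the outside comparison in Section 11.7 alongside the table.

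The cost is one added data field, the reconciled collection wording, and one table. The drawback is wide intervals and possible unblinded reporting bias, both of which should be stated with the table.

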11.8 Responsibility for Data Submission

Data are to be submitted via OnCore on a real-time basis, but no less than once every 2 weeks.

11.9 Data and Records

Primary source documents will include forms routinely used at the Stefanie Spielman Comprehensive Breast Center, namely the Breast Patient Information Form, clinic and office notes as well as laboratory and radiology reports, including documentation found in the electronic medical record (EPIC).

11.10 Safety and Monitoring

Adverse events will be monitored by self-reporting of signs and symptoms.

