4.2. Study Location and Sample

This study will be open for accrual at the Stefanie Spielman Comprehensive Breast Center and James Cancer Hospital. This trial will be conducted under the auspices of The Ohio State University. Testing will take place in clinics of the Stefanie Spielman Comprehensive Breast Center or done so virtually via phone and/or video calls. Patient eligibility will be determined according to the eligibility criteria listed. The study will enroll up to approximately 50 patients.

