The HFRDIS, Daily Hot Flash Score, and OCEAN survey will be administered on paper or virtually via RedCap survey distribution at baseline. Participants will be given paper Daily Hot Flash Score sheets for their own use. For study data collection, electronic surveys will be sent by email via Research Electronic Data Capture (REDCap) for daily and weekly hot flash assessments and the post-treatment satisfaction and efficacy questionnaires. Survey reminder emails and phone calls from study team will be sent to participants for incomplete HFRDIS surveys and satisfaction and efficacy assessments. If a participant initiated the daily surveys on paper prior to the study team using electronic data collection, she will continue using paper assessments for the duration of the study. If assessments are incomplete at end of intervention, the study coordinator will utilize paper forms to collect assessments, as appropriate.

Virtual enrollment will be presented as an option to eligible participants. In this option, calls (phone and/or video) will be done between the research coordinator and participant to discuss the study; screen for eligibility; discuss the informed consent and how to sign it; orient the patient to the device and associated smart phone application; and discuss how to return the device at the conclusion of the device usage. The informed consent document will be sent to the participant to sign via email or mail to obtain a pen signature after the participant has verbally agreed to participate in the study during the call. In addition to either receiving the signed informed consent form via email or mail, the participant will also be able to email the full picture of their signed informed consent form to the study coordinator's email and this will serve as a third option of informed consent documentation. After the consent document is signed, randomization will be done and the research coordinator will then inform the patient the

[Type here]

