7.0 TREATMENT PLAN

7.1 Treatment Plan and Overview

Eligible patients will be approached by study personnel in the clinics at Stefanie Spielman Comprehensive Breast Center, the James Cancer Hospital, and the Center for Women's Health at the Ohio State University Wexner Medical Center. The person obtaining informed consent will tell the patient that 1) participation is voluntary, 2) participation or non-participation will not affect their usual care and management, and 3) patient confidentiality will be maintained in the event that the results of the study are published. The potential toxicities associated with EMBr Wave will be explained fully to the patient. Patients will be provided with a consent form to review, and all questions will be answered. After the signed informed consent has been obtained, a study identification number will be assigned to the patient for use on all data collection forms and samples. Medications and supplements will be reviewed with participants. Research team members may periodically call participants on the phone to remind them to complete the study surveys and to see if the participants are having any problems with the watch.

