7.2 Study Calendar

Informed consent, randomization		
	Group A	Group B
Day 0	
• Receive EMBr Wave• EMBr Wave orientation with introduction to device and mobile application• HFRDIS questionnaire• Daily Hot Flash Score• OCEAN psychographic survey	
• HFRDIS questionnaire• Daily Hot Flash Score• OCEAN psychographic survey
Days 1–28	
• Daily Hot Flash Score• Device usage assessment	
• Daily Hot Flash Score
Days 7, 14, 21, 28	
• HFRDIS questionnaire	
• HFRDIS questionnaire
Day 28	
• Return EMBr Wave• Patient satisfaction / perceived efficacy assessment	
• Receive EMBr Wave• EMBr Wave orientation with introduction to device and mobile application
Days 29–56	
• Daily Hot Flash Score	
• Daily Hot Flash Score• Device usage assessment
Days 35, 42, 49, 56	
• HFRDIS questionnaire	
• HFRDIS questionnaire
Day 56		
• Return EMBr Wave

[Type here]

		
• Patient satisfaction / perceived efficacy assessment
--	--	--

In addition, patients will record their Daily Hot Flash Score daily in their journals.

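### No scheduled adverse event enquiry is specified, so mild or moderate device reactions may be captured incompletely and unevenly, and a low count would be weak evidence of low toxicity

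*Combined protocol and SAP*

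**What the plan says.** Three sections describe how adverse events come to the study team's notice.

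- Section 5.0: "Toxicity will be monitored during study visits and telephone calls", graded by CTCAE version 5.0. No timing is given.
- Section 7.1: "Research team members may periodically call participants on the phone". One stated purpose is survey reminders; the other is "to see if the participants are having any problems with the watch". These calls are permitted, not required.
- Section 11.10: "Adverse events will be monitored by self-reporting of signs and symptoms". No form, prompt or interval is named.

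The calendar in 7.2 covers Days 0 to 56 in both groups. It lists device receipt and return, orientation, HFRDIS, Daily Hot Flash Score, OCEAN, device usage and satisfaction or perceived efficacy. It closes with a note on the daily journals: "In addition, patients will record their Daily Hot Flash Score daily in their journals". No day carries an adverse event or toxicity item.

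Section 4.4 provides other contacts, but for other purposes: "Survey reminder emails and phone calls from study team will be sent to participants for incomplete HFRDIS surveys and satisfaction and efficacy assessments". Section 4.2 allows testing in clinic or "done so virtually via phone and/or video calls". Sections 9.2, 9.3 and 11.12 require adverse events to be collected and documented, without saying how or when participants are asked.

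**The concern.** Section 5.0 reads as if there were regular contacts at which toxicity is assessed, but the rest of the plan does not schedule them. A participant may enrol virtually, receive the device by post and complete every survey electronically. After the orientation call, her only certain contact is then surveys that, as described, do not ask about reactions. Whether she is asked about a sore or irritated wrist depends on whether somebody happens to call.

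This matters for a device worn day and night (4.5), with nickel allergy as an exclusion (4.1.2), no earlier clinical study in breast cancer (3.2) and a second-generation model introduced during the trial (1.1 Trial Design). Section 5.0 expects hardly any toxicity, and incomplete capture pushes the recorded count in that direction whatever the true rate.

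Two functions see only what has been captured: the risk/benefit review in 11.7, and the IRB notification in 11.13 of events that are non-serious but unexpected and possibly related. Because 11.13 covers non-serious events, missed low-grade reactions have a consequence beyond description.

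**Working it through.** **Text check.** The documents state no adverse event rate or safety precision, so there is no figure of the plan's own to reproduce. The point rests on setting the sections side by side:

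| Possible route of detection | Where | Scheduled? | Asks about reactions? |
|---|---|---|---|
| Study visits | 5.0 | No adverse event item on any day in 7.2; contact may be remote (4.2) | Said to monitor toxicity; no question given |
| Optional calls | 7.1 | No | Yes, in general terms: problems with the watch |
| Survey reminder calls | 4.4 | Only for incomplete surveys | Not stated |
| Orientation call (virtual enrolment) | 4.4 | At device receipt | Not stated, and precedes use |
| Weekly and daily surveys | 4.4, 7.2 | Yes | Not described as doing so |
| Self-report | 11.10 | No | Not stated whether prompted |

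The one route with a fixed timetable during use, the surveys, is not described as asking about reactions. The one route with a stated device enquiry has no timetable.

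**Illustration of size.** Inputs: n = 50 (section 4.2), and a capture probability s that the documents do not give. The values of s below are assumptions.

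One-sided 95% upper bound for zero events in n: 1 − 0.05^(1/n).

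- n = 50, full capture: 1 − 0.05^(1/50) = 5.8%.
- Dividing by s: 5.8% / 0.75 ≈ 7.8%; 5.8% / 0.50 ≈ 11.6%; 5.8% / 0.25 ≈ 23.3% (computed from the unrounded 0.05816).

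Conversely, if the true reaction rate were 10% (also an assumption), the chance of recording none is (1 − 0.10s)^50:

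- s = 1: 0.90^50 = 0.5%
- s = 0.50: 0.95^50 = 7.7%
- s = 0.25: 0.975^50 = 28.2%

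The chance of recording at most one event is 3.4%, 27.9% and 64.4% respectively.

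**Reach of a change.** Section 1.1 (Trial Design) reports 23 participants enrolled and none active in follow-up at the amendment, which leaves 50 − 23 = 27. With full capture in those 27, zero events gives 1 − 0.05^(1/27) = 10.5%.

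**The case against.** A reader might infer that reactions surface only if a woman volunteers them. The documents do not support that. The sentence in 7.1 that makes calls optional also says they check for problems with the watch. In 11.10, self-report names the source of the information; it does not say that reporting is unprompted. The calendar is also not a full list of study activities: it omits the chart abstraction of 4.6 and the medication review of 7.1. A missing row shows a missing schedule, not missing monitoring.

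A reader might also infer that the trial could not support a safety conclusion it sets out to draw. It sets out to draw none. Safety is not among the objectives in section 2.0, and section 12 has no safety endpoint or test. The low toxicity in 5.0 is a prior expectation, and the protocol says it will monitor regardless.

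Nor do the documents suggest that the removal rule for related Grade 3-4 reactions would fail. Grade 3 is defined by significant impairment. Such events would probably surface through the medical record (9.2, 11.12) or the oversight in 11.7. Group A's lack of listed contacts after Day 28 matters little for device reactions, because the device has been returned.

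Finally, the capture probabilities are not evidence about this trial. They show only how under-capture widens a bound.

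All of this stands and limits the point. It does not remove it: no section says when or with what question participants are asked, and oversight can review only what has been recorded.

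**Conclusion.** The point holds as a gap in ascertainment: no scheduled adverse event enquiry is specified, and 5.0, 7.1, 7.2 and 11.10 do not fit together. The likely loss is mild or moderate device reactions, captured incompletely and unevenly between participants. A low recorded count would be weak evidence for the expectation in 5.0, and the reviews under 11.7 and 11.13 would work from an incomplete record. Planned efficacy and feasibility analyses are untouched.

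The true size is unknown because no capture rate is given. The bounds of 7.8%, 11.6% and 23.3% are illustrations under assumed capture of 75%, 50% and 25% for a hypothetical 0/50. The finding does not depend on them.

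A related inconsistency bears on what a count would mean. Section 5.0 reports as adverse events only related Grade 3-5 toxicities, whereas 9.3 says all adverse events are collected, and explains this by gait, balance and neuropathy testing that is not part of this trial. These passages must be reconciled. The change is worth making because it is cheap; it is an improvement to the plan, not a condition for the trial's validity.

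**What to change.** For participants still to be enrolled (about 27 of 50):

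1. Add one or two standard items to the weekly survey already completed on Days 7 to 56 in both groups: any new symptom since the last survey, and any wrist-skin problem or discomfort. Pass any yes to the coordinator for CTCAE grading and attribution under 9.1 and 9.2.
2. Add the corresponding row to the calendar in 7.2.
3. Reconcile 5.0, 7.1, 9.3 and 11.10, including whether all adverse events or only related Grade 3-5 events are recorded.
4. Report events descriptively by device and no-device period. State that ascertainment differed for the first 23 participants and that reporting was unblinded. Because the change in questioning would roughly coincide with the move to the Generation 2 device, a difference in counts between generations should not be read as a device difference.

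The cost is one or two items on an existing survey, plus protocol wording. There will be more low-grade events to record. Asking about the wrist in an unblinded trial will prompt some reporting; putting the same question in both periods shows how much is reported without the device, but does not remove that bias.
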